6.2. Subject Disposition

All subjects who discontinue from the study will be identified, and the extent of their participation in the study will be reported. If known, a reason for their discontinuation will be given. A disposition table for all enrolled subjects will be provided.

6.3. Subject Characteristics

The subject's age, sex, weight, height, racial designation, or other demographic and study disease characteristics will be recorded and summarized, and may be used in the pharmacokinetic, pharmacodynamics, and safety analyses as quantitative or classification variables.

6.4. Treatment Compliance

The IP will be administered at the clinical site, and documentation of treatment administration will occur at the site. No analysis for treatment compliance will be performed.

6.5. Concomitant Therapy

In the event medication is used, the name of the drug, the dose and the dosage regimen will be recorded in the CRF. Concomitant therapies will be listed.

6.6. Primary Outcome and Methodology

The primary study objective is to assess target neutralization of CGRP following a single IV dose of LY3316531 versus placebo in healthy subjects via capsaicin-induced DBF as measured using LDI.

The primary objective is measured as decrease from baseline within 30 days, relative to placebo, in capsaicin-induced DBF (by blocking CGRP) following at least 1 dose level of a single IV dose of LY3316531. The primary objective is framed as the alternative hypothesis H_a of the hypothesis-testing construct,

$$H_0: \mu_{LY} = \mu_{Pbo} \text{ versus } H_a: \mu_{LY} > \mu_{Pbo}$$

where μ_{LY} and μ_{Pbo} represent the true mean reduction from baseline in capsaicin-induced DBF.

Statistical significance will be assessed using one-sided, two-sample t -tests with significance established with a p -value less than 0.10. The test statistic, t , is the Behrens-Welch test statistic evaluated as a Student t quantile with degrees of freedom using Satterthwaite's approximation, and has the form,

$$t = \frac{\bar{y}_{LY} - \bar{y}_{Pbo}}{\sqrt{\frac{s_{LY}^2}{n_{LY}} + \frac{s_{Pbo}^2}{n_{Pbo}}}}$$

where n_i is the sample size and

$$s_i^2 = \frac{\sum_{j=1}^{n_i} (y_{ij} - \bar{y}_i)^2}{n_i - 1}$$

is the sample variance for treatment group $i = LY, Pbo$.

It may not be reasonable to assume the treatment groups have similar variance, therefore Satterthwaite's approximation will be used to approximate the degrees of freedom, which is given by

$$df = \frac{\left[\frac{s_{LY}^2}{n_{LY}} + \frac{s_{Pbo}^2}{n_{Pbo}} \right]^2}{\frac{\left(s_{LY}^2/n_{LY} \right)^2}{n_{LY}-1} + \frac{\left(s_{Pbo}^2/n_{Pbo} \right)^2}{n_{Pbo}-1}}$$

The test statistic will be computed for Visits 3 and 4 (post-baseline visits within 30 days of dosing). No correction for multiplicity will be applied, as is customary in Phase 1 trials.

In the event additional cohorts are recruited, subjects assigned to similar treatment arms will be pooled to assess the primary analysis. This includes subjects who are assigned to placebo, and (if applicable) subjects who are assigned to the same LY dosage.

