- i All subjects will have the capsaicin challenge and LDI procedure (pre-challenge and 30 and 40 minutes post-challenge) during a second screening day, V2, and subsequent postdose visits resulting in up to 10 total capsaicin challenges per subject. For each subject, DBF will be measured consistently on the same arm at all study visits.
- j If a subject discontinues from the study early, capsaicin challenge and LDI measurements may be performed at ED if possible, if deemed appropriate by the investigator, and if the most recent capsaicin challenge and LDI measurements for that subject were conducted 7 or more days prior to the ED visit.

3. Introduction

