6.1. Inclusion Criteria

Subjects are eligible for inclusion in the study only if they meet all of the following criteria at screening and/or enrollment:

- [1] are overtly healthy males, as determined through medical history and physical examination
- [2] agree to either remain abstinent (if this is their preferred and usual lifestyle) or use condoms with spermicide as well as 1 additional highly effective method of contraception or effective method of contraception during the study and for 5 months following the last dose of study drug
- [3] are between 18 and 55 years of age, inclusive, at the time of screening
- [4] have a body mass index of 18 to 32.0 kg/m², inclusive, and a minimum body weight of 50 kg
- [5] have clinical laboratory test results within normal reference range for the population or investigative site, or results with acceptable deviations that are judged to be not clinically significant by the investigator
- [6] have venous access sufficient to allow for blood sampling and administration of the investigational product (IP) for IV administration as per the protocol
- [7] have suitable skin characteristics for the dermal capsaicin challenge (as determined by clinical-staff judgment) and have demonstrated at least a 100% increase in dermal flow following capsaicin challenge as part of the screening procedures and measured through LDI
- [8] are reliable and willing to make themselves available for the duration of the study and are willing to follow study procedures
- [9] are able and willing to give signed informed consent

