10.1. Sample Size Determination

The choice of sample size was based on the statistical power to meet the primary endpoint for a single cohort. CCI [REDACTED]

CCI [REDACTED]

A 1-sided significance level of $\alpha = 0.10$ and a standard deviation of 1.322 are assumed. CCI [REDACTED]

A 2-sample t-test with unpooled variance estimates (using Satterthwaite's approximation to the degrees of freedom) is used to compute the power. CCI [REDACTED] CCI [REDACTED]

CCI [REDACTED]

Statistical power may be increased for the LY3316531 dose used in Cohort 1 if a like dose is used in the optional Cohort 2 and the data are combined across cohorts.

In addition to statistical power, 12 LY and 4 Pbo subjects were chosen to be enrolled in Cohort 1 and 9 LY and 3 Pbo subjects were chosen to be enrolled in the optional Cohort 2 for operational reasons and to ensure a satisfactory number of evaluable subjects, reducing the need to replace subjects.

CCI

CCI

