6.1. General Considerations

Data analyses will be provided by treatment groups and for all study subjects combined wherever appropriate. For continuous variables, summary statistics will include number of subjects, mean, median, standard deviation, minimum, and maximum. Categorical endpoints will be summarized using number of subjects, frequency, and percentages. The interpretation of the study results will be the responsibility of the investigator with the pharmacokineticist and statistician. Summary tables, data listings and graphs will be produced with SAS version 9.4, and R version 3.5 or newer will be used for inferential and exploratory analyses. Other software, such as Spotfire, may be used as appropriate to aid the team in decision-making, at the discretion of the statistician and statistical analyst.

Treatment groups will be defined as the LY3316531 dose or placebo. The placebo group will include placebo subjects from all cohorts, if applicable.

Unless otherwise specified, baseline will refer to value collected at the baseline time point. This is usually the value prior to first dosing occasion within the dosing period. In case a specific baseline value is missing, the value at the nearest time point will be used, provided that it is before first dosing. If there are no measurements before dosing then the baseline will be missing.

Unless otherwise specified, missing data will not be imputed and kept missing in the data analyses.

Pharmacokinetic/Pharmacodynamic analyses will be conducted on data from all subjects who receive a dose of LY3316531 and have evaluable PK, total CGRP, or LDI data.

Safety analyses will be conducted for all enrolled subjects, whether or not they completed all protocol requirements.

All protocol deviations that occur during the study will be considered for their severity and impact, and will be taken into consideration when subjects are assigned to analysis populations prior to database lock and unblinding. Details of subject assignment to the analysis populations will be listed.

Additional exploratory analyses of the data will be conducted as deemed appropriate. Study results may be pooled with the results of other studies for population PK analysis purposes to avoid issues with post hoc analyses and incomplete disclosures of analyses.

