6.9. Interim Analyses and Data Monitoring

A single interim analysis that includes all safety and LDI data, and may include PK data, through 23 days post dose (Day 24) will inform the decision to proceed to Phase 2. The interim analysis will be based on the highest dose level evaluated (either Cohort 1 or optional Cohort 2, if implemented).

Note that the primary objective will have complete data at the time of the interim analysis, and therefore the analysis will be the same as described in the above sections. Safety analyses will also be unchanged at interim, but all safety visits may not be complete at the time the interim occurs. All available data will be summarized as described in the sections above.

The decision whether or not to add an additional patient cohort may be made as early as 9 LY and 3 Pbo subjects with Visit 3 data, however it is planned that all subjects will have completed Visit 4 (same as the timing for the interim analysis). The analyses will be the same as described in Section 6.6.

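### Cheap improvement, not an error: the valid primary Welch test could be adjusted for the screening capsaicin response, for a modest power gain at 12:4 if its correlation with the postdose response is low to moderate

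*SAP*

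**What the plan says.** SAP 6.6 sets the hypotheses on means that "represent the true mean reduction from baseline in capsaicin-induced DBF". It tests them with a one-sided two-sample t-test at 0.10, separately at Visits 3 and 4. The statistic uses only group means, variances and sizes. The reason given for unpooled variances is: "It may not be reasonable to assume the treatment groups have similar variance".

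Every enrolled subject should have a predose capsaicin response. Inclusion criterion 7 (Protocol 6.1) requires that subjects "have demonstrated at least a 100% increase in dermal flow following capsaicin challenge as part of the screening procedures". Note i of the Protocol Schedule of Activities places challenges "during a second screening day, V2, and subsequent postdose visits", up to ten in all. Screening, Day 2 (24 to 32 hours after the start of infusion) and Visits 3 to 10 make 1 + 1 + 8 = 10, so screening is the only predose challenge.

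SAP 6.3 says that subject characteristics "may be used in the pharmacokinetic, pharmacodynamics, and safety analyses as quantitative or classification variables", but no section names a covariate for the primary test. Protocol 10.1 says that "a standard deviation of 1.322 are assumed"; the surrounding text is redacted. Protocol 10.3.3 names both absolute and percentage change, and SAP 6.6 does not choose between them.

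**The concern.** Subtracting baseline fixes its coefficient at 1. When baseline and postdose values correlate only weakly or moderately, subtraction adds baseline noise to the outcome, and a fitted coefficient removes it. With 4 placebo subjects in Cohort 1, that precision matters. The same analysis informs the decision to proceed to Phase 2 (SAP 6.9) and the choice about Cohort 2. A value already collected might therefore raise the chance of detecting a real effect without more subjects.

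**Working it through.** **Inputs from the documents.** 12 LY and 4 placebo; one-sided alpha 0.10; SD 1.322; Welch test with Satterthwaite degrees of freedom.

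**Assumptions not in the documents.** 1.322 is the SD of absolute change in enrolled subjects; pre and post SDs are equal before selection; data are normal; the baseline-postdose correlation (rho) ranges from 0.3 to 0.9.

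**The plan's own figure.** The power above 80% cannot be reproduced because the effect size is redacted. Instead, the effect giving Welch 80% power was solved for:
- Variance terms: 1.322²/12 = 0.1456 and 1.322²/4 = 0.4369, sum 0.5826, so the SE is 0.763.
- Degrees of freedom: 0.5826² / (0.1456²/11 + 0.4369²/3) = 5.2.
- Difference for 80% power: 1.77 by the noncentral t; 1.78 was used in the simulations.

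**Expected gain in variance.** With equal SDs (s) and a common slope, the change has variance 2s²(1 - rho) and the adjusted residual s²(1 - rho²). The ratio is (1 + rho)/2. Estimating the slope costs a factor 1 + 1/(N - 4) = 13/12 at N = 16.

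| rho | (1 + rho)/2 | × 13/12 |
|---|---|---|
| 0.3 | 0.65 | 0.70 |
| 0.5 | 0.75 | 0.81 |
| 0.7 | 0.85 | 0.92 |
| 0.9 | 0.95 | 1.03 |

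Break-even is at a ratio of 12/13 = 0.92, that is rho = 2 × 12/13 - 1 = 0.85.

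**Simulated power at 12:4** (20,000 trials per cell, Monte Carlo SE about 0.3 points). The adjusted model regresses reduction on treatment and screening response, with REML group variances and Satterthwaite degrees of freedom. Cells show Welch to adjusted, in percent. The effect is held at 1.78, so Welch power moves away from 80% when the LY slope or SD changes.

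| Scenario | rho 0.3 | 0.5 | 0.7 | 0.8 | 0.9 |
|---|---|---|---|---|---|
| No selection, common slope | 80.3 to 88.6 | 80.1 to 85.6 | 79.2 to 81.9 | 80.0 to 80.6 | 79.9 to 78.9 |
| Lower 25% of baseline removed | 79.9 to 84.1 | 80.1 to 82.6 | 79.3 to 79.6 | 80.2 to 79.4 | 80.0 to 78.5 |
| Lower 50% removed | 79.7 to 82.2 | 80.2 to 81.2 | 79.4 to 78.8 | 80.3 to 78.9 | 80.0 to 78.2 |
| LY residual SD doubled | 69.9 to 75.3 | 68.5 to 70.8 | 67.3 to 66.6 | 66.5 to 64.6 | 66.2 to 63.7 |
| LY slope halved | 79.1 to 88.7 | 78.4 to 84.5 | 77.3 to 78.9 | 76.0 to 73.5 | 73.1 to 64.0 |
| LY slope and residual SD halved | 81.9 to 92.2 | 81.1 to 88.0 | 80.4 to 82.0 | 79.7 to 76.2 | 76.8 to 64.7 |

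Smaller runs with LY slope and residual SD both cut by 70% gave gains of 7 to 11 points at rho 0.3 to 0.5. The change was between 0 and -2 at 0.7, and the loss was 18 to 19 points at 0.9 (72.5 to 53.1 in one run).

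**Type I error (nominal 0.10).** In the 20,000-trial null runs the adjusted model at 12:4 gave 0.092 to 0.106, and Welch gave 0.092 to 0.109 over all designs. Ordinary pooled-variance ANCOVA gave about 0.15 to 0.21 when the placebo postdose SD was 1.5 to 3 times that of LY.

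**The case against.** The strongest case against is that nothing here is a defect. Welch on change tests the stated hypothesis directly, and the SAP gives its reason for that choice. Additional exploratory analyses are already allowed. This stands: a reader might infer that the planned test is wrong, biased or underpowered, and the documents support none of these.

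The gain also rests on inputs that cannot be seen. The correlation is not given, and the scale behind 1.322 is redacted. If the endpoint is percentage reduction, baseline already enters by division and the figures above do not carry over. This stands, and is why the point is conditional.

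Protocol 5.5 says the dose was chosen to produce maximal effect. Strong inhibition may flatten the LY slope, in which case adjustment loses materially at high correlation. This also stands; the simulations confirm it.

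Timing is a further limit. Protocol 10.3.6 unblinds the sponsor team at the Cohort 1 reviews. The current protocol (approved February 2019) refers in 5.4 to a PD effect already noted in this study, and its amendment rationale cites Day 120 data. Changing the primary test after seeing treatment-level data would be worse than losing a few points of power.

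One might also rest the case on the 9:3 look, but SAP 6.9 treats that as the earliest option: "however it is planned that all subjects will have completed Visit 4".

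These objections limit the recommendation but do not remove it. The adjustment uses data already collected, keeps unequal variances, and can be checked before it is adopted.

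**Conclusion.** A conditional, low-cost improvement to SAP 6.6. On absolute reduction, with 1.322 as the SD of change and an effect giving Welch 80% power at 12:4, adjustment adds about 8 points at rho 0.3, 6 at 0.5 and 2 to 3 at 0.7, and loses about 1 at 0.9. If criterion 7 removes the lower quarter of baseline responses, the gain is roughly halved at rho 0.3 to 0.5 and is close to zero at 0.7.

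In the 12:4 scenarios run, the loss at rho 0.7 or below is at most about 2 points. At rho 0.9 it is about 9 points with the LY slope halved, 12 with slope and residual SD halved, and up to about 20 with both cut by 70%. A reader might take the +8 as the expected benefit. It is the no-selection, low-correlation case, and the documents do not show that it applies.

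**What to change.** 1. Before the sponsor team is unblinded, take the sponsor's earlier capsaicin data if available (for example the galcanezumab study in Protocol 3.2). Restrict them to subjects who would meet criterion 7 and use the endpoint's own scale. Estimate the correlation, and the slope and residual SD in each arm.
2. Simulate both tests at 12:4 with those values.
3. If the adjusted model has at least Welch's power, specify it in SAP 6.6 for Visits 3 and 4: reduction on treatment and predose screening capsaicin-induced DBF, group-specific residual variances by REML, Satterthwaite degrees of freedom, one-sided 0.10. Pool placebo if Cohort 2 runs, in line with SAP 6.1 ("The placebo group will include placebo subjects from all cohorts, if applicable"). Keep Welch as the sensitivity analysis and for any early 9:3 look.
4. Otherwise keep Welch as primary.
5. Do not use pooled-variance ANCOVA.
6. Define the covariate as the screening capsaicin response, so that it is not confused with the pre-capsaicin reading taken at each visit.
7. For data already unblinded, report the adjusted model only as a labelled supportive analysis.

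The cost is one look at existing data, a short simulation, a few lines of SAP text and code, and one extra model parameter. No new measurements are needed.

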6.7. Bioanalytical and Pharmacokinetic/Pharmacodynamic Methods

All PK and PK/PD analyses will be performed by Lilly Global PK/PD/PMx. Details will be included in a separate analysis plan and/or described in the clinical study report (CSR).

6.8. Safety Analyses

Safety parameters that will be assessed include safety laboratory parameters, vital signs, and ECG parameters. The parameters will be listed, and summarized using standard descriptive statistics. Additional analysis will be performed if warranted upon review of the data. Baseline for safety parameters will be defined as the last evaluable value before the first dose for each subject.

6.8.1. Adverse Events

All IP and protocol procedure AEs will be listed, and if the frequency of events allows, safety data will be summarized using descriptive methodology.

The discontinuations due to adverse events will be listed. The serious adverse events (SAEs), the severe treatment emergent adverse events (TEAEs), the adverse events occurring on or after signing study informed consent document and the pre-existing conditions will be listed.

Adverse events reported to occur prior to enrollment will be distinguished from those reported as new or increased in severity after enrollment which will be classified as TEAEs. The incidence of TEAEs for each treatment group and total LY will be presented by system organ class (SOC) and preferred term (PT), by severity and by association with investigational product as perceived by the investigator. A table will present the frequency of subjects with TEAEs by Week. The frequency of subjects with TEAEs will be presented by treatment group, by preferred term. Each symptom will be classified by the most suitable term from the medical regulatory dictionary.

6.8.2. Clinical Laboratory Evaluation

The safety laboratory parameters will be listed and summarized using standard descriptive statistics per treatment group.

6.8.3. Vital Signs and Other Physical Findings

Vital signs including pulse rate, SBP, DBP and body temperature will be listed. There will be a table summarizing vital sign parameters (pulse rate, SBP, DBP) by treatment group and by time. A table presenting the mean change from baseline supine vital sign parameters (pulse rate, SBP, DBP) by treatment group for each of these time points: Day 1 (including predose, end of infusion, and 2, 6, and 12 hours after start of infusion), Day 2 (24 hours after start of infusion), and Days 10, 24, 38, 52, 66 and 80 will be presented. The table may be split in to multiple tables, by time, if necessary to easily view the data.

6.8.4. Electrocardiograms

ECG parameters will be listed and summarized by treatment group and time. Mean changes from baseline for QT and QTcF parameters will be summarized by treatment group and by time (Day 1: predose, end of infusion, and 6 hours after start of infusion; and Day 2: 24 hours after start of infusion). A table of frequency of QT and QTcF >500 msec at any time point will be provided by treatment group. A table of frequency of mean change from baseline of QT and QTcF >60 msec at any time will be presented by treatment group. A Graph of mean changes from baseline QT and QTcF versus time by treatment group and a graph of mean changes from baseline QT and QTcF versus LY3316531 concentration by time will be provided.

6.9. Interim Analyses and Data Monitoring

A single interim analysis that includes all safety and LDI data, and may include PK data, through 23 days post dose (Day 24) will inform the decision to proceed to Phase 2. The interim analysis will be based on the highest dose level evaluated (either Cohort 1 or optional Cohort 2, if implemented).

Note that the primary objective will have complete data at the time of the interim analysis, and therefore the analysis will be the same as described in the above sections. Safety analyses will also be unchanged at interim, but all safety visits may not be complete at the time the interim occurs. All available data will be summarized as described in the sections above.

The decision whether or not to add an additional patient cohort may be made as early as 9 LY and 3 Pbo subjects with Visit 3 data, however it is planned that all subjects will have completed Visit 4 (same as the timing for the interim analysis). The analyses will be the same as described in Section 6.6.

6.10. Planned Exploratory Analyses

In the event that an additional cohort is chosen (Cohort 2), and the dose of LY to be administered is the same across cohorts, an analysis of the primary endpoint with pooled responses across cohorts for subjects randomized to the same treatment group (placebo, 300mg LY) will be

performed. If the protocol allows for the pooled analysis, this will be part of the primary (see Section 6.6 for full details).

Other exploratory analyses will be performed by PK/PD and LEM functions.

6.11. Clinical Trial Registry Analyses

Additional analyses will be performed for the purpose of fulfilling the Clinical Trial Registry (CTR) requirements.

Analyses provided for the CTR requirements include the following:

Summary of adverse events, provided as a dataset which will be converted to an XML file. Both Serious Adverse Events and ‘Other’ Adverse Events are summarized: by treatment group, by MedDRA preferred term.

- An adverse event is considered ‘Serious’ whether or not it is a treatment emergent adverse event (TEAE).
- An adverse event is considered in the ‘Other’ category if it is both a TEAE and is not serious. For each Serious AE and ‘Other’ AE, for each term and treatment group, the following are provided:
 - the number of participants at risk of an event
 - the number of participants who experienced each event term
 - the number of events experienced.
- Consistent with www.ClinicalTrials.gov requirements, ‘Other’ AEs that occur in fewer than 5% of patients/subjects in every treatment group may not be included if a 5% threshold is chosen (5% is the minimum threshold).
- AE reporting is consistent with other document disclosures for example, the CSR, manuscripts, and so forth.

Leo Document ID = 30ea3a78-81d3-4637-9651-11db333f819d

Approver: PPD

Approval Date & Time: 17-Oct-2018 15:00:10 GMT

Signature meaning: Approved
